10.3.2.2 Serious infections

Serious infections are generally defined as those that result in death, are life-threatening; require inpatient hospitalisation or prolongation of existing hospitalisation; require treatment with IV antimicrobials (e.g., antibiotics, antifungals, antivirals); result in persistent or significant disability/incapacity; or are, based upon appropriate medical judgement, important medical events that may not be immediately life-threatening or result in death or hospitalisation but may jeopardise the patient or may require intervention to prevent one of the other outcomes listed above [22, 27]. It may not be possible to identify all serious infections using this definition since it is not possible to assess some of its components from the secondary data sources e.g., if a particular infection prolonged an existing hospitalisation or led to disability.

Thus, for current study, the **primary outcome** serious infection will be defined as infections leading to hospitalisation, use of IV antimicrobials, or death. It will be defined as either of:

- Infections leading to hospitalisation:
 - Infection diagnosis as part of a hospitalisation episode (including primary and secondary diagnoses) (Table 16) [8, 78]
 - Infection diagnosis in primary or secondary care settings up to 7 days before hospitalisation (Table 16) [9, 79]

⁵The specific malignancies were defined based on the previously described increased or decreased risk among SLE patients when compared to the general population [12, 13, 84].

- Infections requiring treatment with IV antimicrobials:
 - Prescription/administration of IV antimicrobials (Table 19) [46, 51]
- Infection-related death:
 - Recorded diagnosis of infection (Table 16) in primary or secondary care settings with record of death within the subsequent 30 days [30].

Detailed operational definitions to identify the availability of serious infections data in different data sources as disease coding systems used will be defined in the SAP.

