The socio-economic registers cover a wide range of information on residents in Denmark. These include annual income by individual or family, highest achieved education, occupation, proportion of time outside employment due to sick leave etc., and information on individuals receiving different types of disability aid. Socio-economic registers at Statistics Denmark are updated annually, typically after December.

Study-specific data

In Denmark, market launch of anifrolumab occurred in May 2022 (Table 3). It is assumed that information on anifrolumab will be available in SMR as it is administered in hospital settings, and information on belimumab (a proxy) is captured in this registry. ATC codes and Danish brand names allow the distinction between biologics. Information on SLE SOC dispensed in retail pharmacies is available through RMPS (since 1995) and drugs administered in hospital are available through SMR.

Data on malignancies (overall and sub-types) are captured through ICD-O diagnoses codes from the Cancer Registry. Serious infections are identified at the secondary care level through primary ICD-10 diagnoses, i.e., identified if infections are the reason for contact with the hospital. Data are not available for conditions managed only by a GP or a specialist in private practice. ICD-10 codes allow the identification of specific types of serious infections. Data on prescription/administration of IV antimicrobials are also available in the SMR. Dates of diagnoses, hospitalisation admission, discharge and date of death (regardless of the setting where occurs) are available.

Data on covariates are generally available (Table 26), except for Body Mass Index (BMI) (including weight or height), alcohol consumption, smoking and vaccination history. Procedures with radiation exposure may be available if procedure codes are registered. Previous infections may be available if the diagnosis occurred in secondary care.

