10.4.1.2 France: National Health Data System

The French National Health Data System (*Système National des Données de Santé* [SNDS]) is the largest and most comprehensive healthcare dataset available in Europe. It covers 99% of the total French population - around 66 million patients [14]. Individuals enter SNDS at birth or by immigration and exit at death or emigration.

SNDS includes anonymised administrative and healthcare claims data from the French national health care insurance system databases. In particular, data from several databases are available [83]:

• the French National Health Insurance database (*Système national d'information interrégimes de l'Assurance maladie* [SNIIRAM]), available since 2008;

- the French hospital discharge summaries (*Programme de Médicalisation des Systèmes d'Information* [PMSI]), available since 2006;
- the national death registry (*Centre d'épidémiologie sur les causes médicales de Décès* [CépiDC]).

Since 2008, SNIIRAM includes the outpatient reimbursed health expenditures database (*données de consommation interrégimes* [DCIR]), which allows capturing consumption of care.

Reimbursed drugs dispensed through retail pharmacies are available through DCIR and drugs are identified by their ATC code. The date of dispensing, quantity, and brand name are also available. Information on route of administration is available and dose may be estimated from DDD. Information on drug indication is only possible for the inpatient setting, derived from diagnoses.

Hospital administered treatments are available through PMSI, if they are part of the list of highcost drugs (*medicaments listed en sus*). Inclusion in the list allows the reimbursement of drugs, in addition to the hospital episode reimbursement.

Through the PMSI, SNDS includes medical summaries of all hospitalisations from private or public hospitals, including date of stay, medical procedures, devices implanted during the hospital stay, primary diagnosis (main reason for admission) and related diagnosis. These data are encoded according to the ICD-10.

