10.4.1.3 Germany: Statutory Health Insurance Providers Claims

In Germany, insurance claims from approximately 8-10 different statutory health insurance (SHI) providers are collected by Team Gesundheit. SHI is a requirement for individuals with a permanent place of residence in Germany, even for short-term stays. Since 2012, all individuals in Germany have a specific identifier which would not change throughout lifetime. SHI covers 89% of German population; data available through the Team Gesundheit represents 5-6% of the German population, representative in terms of age, gender and region. This data source has been used for different research purposes, including oncology [18, 36] and rheumatic diseases treated with biologic agents [102].

Data on medications cover prescriptions in primary care and community pharmacy dispensing. Data on medication use in inpatient setting are not available. Data on drugs administered in outpatient visits at the hospital are captured, unless the hospital visit is reimbursed as diagnosisrelated group (DRG). In that case it will not be possible to know which drug was administered as only one generic code will be available. Drug indication is not available since there is no active link between diagnosis and the prescribed therapy. Dose can be derived from the quantity prescribed and the period between prescription dates. Prescription and dispensation dates are available, but not for over-the-counter products and substances not reimbursed.

The database contains information from primary care and in- and outpatient hospital care. Data on physician visits, specialist code of the treating physician (e.g., gastroenterology), and hospitalisations are available. For inpatient stays, primary diagnoses and secondary diagnoses are available, primary diagnoses are a proxy for "cause of hospitalisation".

Diagnosis information is available and captured using the ICD-10 coding system with German modification (GM). Data on surgical and medical procedures are recorded using the GM of the ICD-10-PCS (ICD-10 Procedure Coding System) and the operation and procedure classification system (*Operationen und Prozedurenschlüssel* [OPS]). Due to the nature of the claims data, information on data that are not subject to reimbursement are not visible in the database. For

example, information on symptoms captured by ICD-10 coding would have little or no coverage as they are usually not subject to reimbursement.

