Computations were carried out with two conservative incidence rates for each outcome. Results using the incidence rates in the general population can be considered as a lower bound for the achieved power/minimum required sample sizes. Results using the incidence rates in SLE population can be considered as an upper bound for the achieved power/minimum required sample sizes.

For the malignancy outcome: There are several estimates for incidence rates (IR) of malignancy in the literature. Since this study involves cohorts situated within Europe, IR estimates based on data available within Europe for the general population and an SLE specified population were used (Table 9 and Table 10, respectively).

- Based on data from the European Cancer Information System, in 2012 the overall incidence of malignancy in the general population was 5.26 per 1000 person-years in the UK [31].
- In a multicentre study of a patient cohort from the Systemic Lupus Erythematosus Registry of the Spanish Society of Rheumatology, IR for malignancy in patients with SLE was 6.31 per 1000 person-years [19].

For the serious infection outcome: There are several estimates for IRs of serious infection in the literature. Since this study involves cohorts situated within Europe, we used IR estimates based on data available from Europe. The IR estimates in the general population and in SLE patients specified below were used for the power calculations (Table 11 and Table 12).

• In a study from the Swedish Lupus Linkage cohort, newly diagnosed patients with SLE (2006–2013) and general population comparators were followed for serious infection until

2016. Rates of serious infections in the general population were 9.6 per 1000 person-years and 39.8 per 1000 person-years amongst SLE patients [81]. The definition used for serious infection outcome in this study was hospitalisation with infection as the primary diagnosis using ICD codes from the National Patient Registry of Sweden inpatient database.

Simulation steps

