• The use of different databases (coded hospitalisations, drug prescriptions, death registries) is likely to improve sensitivity of the outcome [8], by identifying serious infections that are managed in different settings (because of the type of infection, countries' healthcare structure or access to care). Infection-related diagnoses in inpatient administrative data sources showed sensitivity ranging from 4.4–100%, depending on the type of infection (e.g., low sensitivity for sepsis), source of data, population included, and the algorithms used [8]. By considering several infection diagnoses and including diagnoses in any position (primary and secondary diagnosis) sensitivity is increased. However, specificity might decrease as infections not related with drug exposure might be more often captured. Although the definition used is likely to have high sensitivity to

capture all serious infections, data from different databases may not be available in all countries, impairing comparability.

- In France, data on IV antimicrobials may not be captured because only expensive drugs administered in the hospital setting are captured. Additionally, only data on hospitalisation diagnoses are available and it is not possible to capture data on infections coded in primary care that resulted in a hospitalisation (if that hospitalisation does not include an infection diagnosis).
- In Germany, data on inpatient IV antimicrobials administration are not captured.
- The Danish National Registries only capture data on diagnoses from secondary care (emergency, inpatient, and specialty outpatient care) and if the infection is coded as the reason for healthcare encounter.

To account for possible misclassification, narrow definitions of serious infection will be used as sensitivity analyses for the primary outcomes, by assessing and comparing the incidence of each component of the serious infection definition. However, these analyses may not be feasible if sample sizes are small for each of these serious infection components. Additionally, the management of serious infections in each country may differ, limiting generalizability.

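### The Danish hospital-infection outcome is primary-diagnosis only while the protocol definition counts primary and secondary diagnoses, and no listed serious-infection analysis puts all four sources on one case definition

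*Protocol*

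**What the plan says.** Section 10.3.2.2 builds the composite from three branches: infection leading to hospitalisation, intravenous (IV) antimicrobials, and infection-related death. The hospitalisation branch includes "Infection diagnosis as part of a hospitalisation episode (including primary and secondary diagnoses" and also infections diagnosed in the week before admission. Section 10.9 repeats the position rule and gives its purpose: by "including diagnoses in any position (primary and secondary diagnosis) sensitivity is increased".

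For Denmark, 10.4.1.1 says "Serious infections are identified at the secondary care level through primary ICD-10 diagnoses". Section 10.9 confirms that Danish diagnoses come from secondary care only "and if the infection is coded as the reason for healthcare encounter". (Secondary care is the setting; the issue here is the position of the code.) For Germany, "For inpatient stays, primary diagnoses and secondary diagnoses are available" (10.4.1.3). For France, 10.4.1.2 lists "primary diagnosis (main reason for admission) and related diagnosis". The Spanish section, 10.4.1.4, does not mention diagnosis position.

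Section 10.7.1.6 enters the country log HRs for the primary objectives into a random-effects inverse-variance model. As the response to misclassification, 10.9 says that "narrow definitions of serious infection will be used as sensitivity analyses for the primary outcomes", meaning each component of the composite taken separately. Section 10.7.1.7 makes these component comparisons conditional on feasibility.

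**The concern.** The outcome that defines primary objectives 3 and 4 cannot be implemented as written in one of the four sources. Both arms within a country share that country's definition, so no country HR is internally inconsistent. The difficulty lies in the pooled HR and in the Q, I² and τ² statistics. They combine estimates of differently defined outcomes, and a gap between Denmark and the rest could reflect coding position rather than a difference in risk.

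The remedy named in 10.9 is meant to deal with misclassification, but it narrows the outcome by component and not by diagnosis position. A reader of the final report would have no protocol-specified result in which serious infection means the same thing in every country.

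**Working it through.** **1. What each source can supply (10.4.1, Table 7, 10.9).**

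| Source | Position of hospital infection code | IV antimicrobials | Diagnoses outside hospital care |
|---|---|---|---|
| Denmark | Primary only (reason for contact) | Recorded, including inpatients | None from general practice or private specialists |
| France | Primary and related | Inpatient, expensive drugs only | Not captured |
| Germany | Primary and secondary | Outpatient only | Captured |
| Spain | Not stated | Recorded | Captured |

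**2. Whether a listed analysis aligns the definition (10.7.1.7).**

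- Biologic and non-biologic comparator groups: the outcome is unchanged.
- Fixed-effect pooling: the outcome is unchanged.
- Component analyses: the hospitalisation component stays primary-only in Denmark and follows the wider rule elsewhere. The IV component differs between France, Germany and the other two. The death component depends on which infection diagnoses a source records.

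None gives one case definition in all four sources.

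**3. Reproducing the protocol's sample size.** Inputs from 10.5.2 and Table 13: 1,312 exposed, split 77 / 978 / 71 / 186 (Denmark, France, Germany, Spain); 1:3 matching; 39.8 per 1,000 person-years; 2 years; HR 1.5; SD(HR) 0.2; p < 0.05, taken as two-sided. The SD on the log scale is 0.2/1.5 = 0.133. Each country log HR is drawn from N(log 1.5, 0.133²). Survival times are exponential, and the country estimate is the log rate ratio with variance 1/e1 + 1/e0, where e1 and e0 are the events in the two arms. Pooling is DerSimonian-Laird. With 4,000 runs:

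- N = 1,312: power 0.79 (protocol 0.80)
- N = 1,500: 0.82 (Table 12: 0.835)
- N = 1,000: 0.74 (Table 12: 0.716)

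The model is close enough to the protocol's to be used for weights.

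**4. Denmark's weight.** Share of expected exposed patients: 89/1,435 = 6.2% (Table 8). Share in Table 13: 5.89%. Mean simulated weight: 5.7% with fixed effects and 9.4% with random effects.

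**5. Effect of a different Danish HR.** The Danish values are assumptions; the other three sources stay at 1.5. By hand with the Table 13 share, pooled HR = exp[0.0589 × log(HR_DK) + 0.9411 × log(1.5)]:

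- HR_DK = 1.2: 1.48
- HR_DK = 1.8: 1.52

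By simulation with random-effects weights (3,000 runs each):

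| Danish HR | Pooled HR |
|---|---|
| 1.0 | 1.45 |
| 1.2 | 1.48 |
| 1.5 | 1.50 |
| 1.8 | 1.55 |
| 2.25 | 1.62 |

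**The case against.** The protocol does not hide this. Section 10.9 names the Danish restriction and says differing databases impair comparability. Section 10.3 allows variable definitions to differ by source, and 10.3.2.2 leaves source-level operational definitions to the SAP, which is not at hand. All of that stands, and it limits the claim about missing analyses to the protocol. It does not rescue the stated remedy, which leaves diagnosis position untouched.

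The composite also closes part of the Danish gap. An infection coded in secondary position but treated with IV antimicrobials can still qualify, because the Danish hospital medication register covers inpatients. This stands, and it is one reason to expect a small effect.

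Country results, forest plots and heterogeneity statistics are all planned, and high heterogeneity triggers a review of its sources (10.7.1.6). A Danish outlier would therefore be seen. Coding position would not be isolated as its cause.

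A reader might go further and infer that secondary-position coding seriously dilutes the HR in the other three sources. If 20%, 30% or 40% of events were incidental with HR 1, a true 1.5 would read 1 + 0.5 × 0.8 = 1.40, 1 + 0.5 × 0.7 = 1.35 or 1 + 0.5 × 0.6 = 1.30, and power would fall. The documents do not support this as a finding. They give no incidental share, and 10.9 says only that specificity might decrease. Such a result would also criticise the any-position definition itself rather than the Danish mismatch. Nor is it documented that the other three sources, 1,346/1,435 = 94% of patients, all hold secondary positions. Only Germany, 126/1,435 = 9%, is described as holding both primary and secondary inpatient diagnoses.

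A reader might also call the planning rate of 39.8 an error. Section 10.5.2 is open about its basis: "The definition used for serious infection outcome in this study was hospitalisation with infection as the primary diagnosis using ICD codes". A broader outcome should yield more events, so this is no mistake in the sample size.

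**Conclusion.** The inconsistency is real, and it is disclosed but not resolved. The definition in 10.3.2.2 cannot be applied as written in Denmark, the pooled HR combines differing case definitions, and the component analyses offered in 10.9 leave the position mismatch in place.

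The direct effect on the pooled estimate is modest. With Denmark at about 6% to 9% of the weight, a Danish HR between 1.2 and 1.8 gives a pooled HR of about 1.48 to 1.55 when the true value elsewhere is 1.5. This rests on the assumed Danish HRs, the Table 13 country shares, and a simulation that reproduces the protocol's power to within about one point at 1,312. The effect of any-position coding in the other sources is unknown. The point concerns the interpretation of the pooled HR and of its heterogeneity; it is not evidence that the study is underpowered.

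**What to change.** In 10.7.1.7, add a sensitivity analysis of objectives 3 and 4 in which the event is a hospitalisation with infection as the primary (main) inpatient diagnosis. Leave out the IV-antimicrobial and death branches, because their capture also differs between sources. Run it in every source that records diagnosis position: Denmark, France and Germany on the protocol's own description, and Spain once confirmed. Pool the objective 4 HRs with the same random-effects model. This also matches the case definition behind the planning rate.

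In 10.3.2.2, state that the Danish hospitalisation component is primary-diagnosis only. Keep the any-position composite as the main analysis.

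The cost is one extra model per source and one extra pooled estimate, with fewer events and a wider interval than the main analysis. Denmark, France and Germany already record what is needed. If Spain does not record position, the pooled sensitivity estimate would cover three sources, and the report should say so.

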10.4.1.2 France: National Health Data System

The French National Health Data System (*Système National des Données de Santé* [SNDS]) is the largest and most comprehensive healthcare dataset available in Europe. It covers 99% of the total French population - around 66 million patients [14]. Individuals enter SNDS at birth or by immigration and exit at death or emigration.

SNDS includes anonymised administrative and healthcare claims data from the French national health care insurance system databases. In particular, data from several databases are available [83]:

• the French National Health Insurance database (*Système national d'information interrégimes de l'Assurance maladie* [SNIIRAM]), available since 2008;

- the French hospital discharge summaries (*Programme de Médicalisation des Systèmes d'Information* [PMSI]), available since 2006;
- the national death registry (*Centre d'épidémiologie sur les causes médicales de Décès* [CépiDC]).

Since 2008, SNIIRAM includes the outpatient reimbursed health expenditures database (*données de consommation interrégimes* [DCIR]), which allows capturing consumption of care.

Reimbursed drugs dispensed through retail pharmacies are available through DCIR and drugs are identified by their ATC code. The date of dispensing, quantity, and brand name are also available. Information on route of administration is available and dose may be estimated from DDD. Information on drug indication is only possible for the inpatient setting, derived from diagnoses.

Hospital administered treatments are available through PMSI, if they are part of the list of highcost drugs (*medicaments listed en sus*). Inclusion in the list allows the reimbursement of drugs, in addition to the hospital episode reimbursement.

Through the PMSI, SNDS includes medical summaries of all hospitalisations from private or public hospitals, including date of stay, medical procedures, devices implanted during the hospital stay, primary diagnosis (main reason for admission) and related diagnosis. These data are encoded according to the ICD-10.

SNDS contains data on the presence and diagnosis date of long-term chronic disease (LTD). LTD is used together with PMSI to identify patients, namely those with SLE. Patients with LTD are eligible for 100% reimbursement of healthcare expenditure. The request for attribution of LTD is made by the general practitioner and it is not mandatory. Thus, it may be missing, for instance, if the medical expenses are already covered by another chronic disease or the treatment is not expensive. Diagnoses are coded using ICD-10.

SNDS also includes demographic data (including age, sex, place of residence, complementary universal health coverage status (as proxy to socio-economic status), date of death), health encounters, dispensations, medical devices, and laboratory tests (without results) [14].

Data from DCIR and PMSI are annually updated and can be linked for each patient. At the time of the feasibility assessment, data were available until the end of 2021.

Study-specific data

In France, market launch for anifrolumab occurred in April 2022 (Table 3). A favourable reimbursement decision has been made by the health assessment authorities in France. Therefore, it is anticipated that anifrolumab will likely be included in the list of high-cost drugs and thus, will be captured in PMSI.

Data on SLE SOC drugs are available, except for voclosporin and mepacrine, which are not marketed in France. Some drugs, such as methotrexate, mycophenolate mofetil, cyclophosphamide, and cyclosporine are available if the oral forms are used. Chloroquine was in

use until the end of September 2022, when the last product was withdrawn from the market. Furthermore, rituximab and immunoglobulin G – administered as IV at the hospital – are available as they are part of the list of high-cost drugs. Only the pen formulation of belimumab, delivered in retail pharmacies, is captured.

Data on overall and specific malignancies are captured through coded diagnoses at the hospital level. This is also true for serious infections in which diagnoses allow for the identification of specific types of serious infections. Data on prescription/administration of IV antimicrobials are available for inpatients if antimicrobials are part of the list of expensive drugs. Dates of diagnoses (inpatients), hospitalisation, discharge and death are available.

Data on covariates are generally available (Table 26), except for BMI (including weight or height), alcohol consumption, and smoking. Vaccination data are captured if reimbursed.

